Some trans women who participate will receive the intervention right away. Others will receive it in six months. Who gets it right away versus later is randomly determined. This is so we can test the effects of the intervention.

If you are randomly assigned to receive the intervention right away, you will come to six sessions on six different days. Each session will last for around 2 ♦ hours (around 15 hours total).

If you are randomly assigned to receive the intervention in 6 months, you will come to three sessions on three different days. Each session will last for around 4 hours (around 12 hours total).

Sessions will be held at VCU or at one of our community partners.

Some participants will also receive some financial assistance for finding a job and for gender transition costs. Who receives that financial assistance will be also randomly determined.

We will audio record the intervention, including what you say when you participate, but we will keep everything you tell us confidential. The intervention is expected to last a total of around 15 hours, spread out over 6 days (2 1/2 hours per day). An incentive of \$15/hour will be paid for your participation. So, if you came to 15 hours, you would receive \$225 and if you come to 12 hours, you would receive \$180.

If you participate, you will also be asked to complete a questionnaire four times. The first time you complete it, we will pay you \$20. That amount will go up by \$5 for each additional time you complete the questionnaire -- \$25 for the second time (3 months later), \$30 for the third time (3 months after that), and \$35 the fourth time (3 months after that). If you complete all four questionnaires, we will give you an additional \$50 bonus.

I ♦ m happy to answer any questions you have. Please let me know if you♦d like to learn more or if you♦d like to participate in the intervention.

Regards,

[name]♦

If contacted, the writer will answer any questions and, if the participant is interested, schedule the interview. If the interview is scheduled more than 1 day after the participant agrees to participate, we will ask their permission to send a reminder text/email/phone call on the day before the interview.

We also asked about other or better means to contact them. These might include being contacted via social media. In that case, we will use the email script (or as close to it as possible if there are space limitations in the social media platform♦s messaging system).

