Randomization. Fifty participants in each study site will be randomized to the intervention or wait-list minimal treatment control group. Assuming 80% retention, this will yield a total sample size of 80 (40 in each site). When assigning participants to treatment/control, we will use urn randomization, an adaptive randomization procedure that ensures approximately equal group sizes while approaching complete randomization.⁹⁴ Adherence to the intervention and supervision of interventionists. Sessions will be conducted in private spaces at our community partner locations according to the guidelines in the treatment manual developed in Aim 2. Facilitators will follow checklists developed for each session and will complete a post-session quality assurance form after each session. All study sessions will be digitally recorded. Study investigators will listen to the first recording of each session and provide feedback to interventionists regarding adherence and quality of administration. Thereafter, study investigators will listen to 20% of all recordings (chosen randomly) and provide feedback as needed. To ensure consistency across study site, investigators will listen to audiotapes and provide feedback for both study sites. Monthly group supervision with interventionists will be conducted by the investigators.

Tracking and retention procedures: As it is common for economically marginalized individuals to move frequently and to be financially unable to maintain consistent phone service, comprehensive tracking information will be collected and updated monthly. This information will include home addresses and phone numbers, but also email addresses, social media account information (e.g., Facebook, Instagram) and contact information for individuals who would know how to reach the participants (e.g., friends, family, health care providers, emergency shelter staff). Participants will also be asked to update contact information at the end of each intervention/assessment session. To increase session attendance, we will offset transportation costs.

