For individuals randomized to the full intervention (Aim 3), in order to increase the likelihood that the intervention is received at the intended dosage (15 hours), participants will be paid \$15/hour for their participation. The intervention is designed to be delivered over 6 days with 2 1/2 hour sessions per day, for a total of 15 hours. Participants that attend 15 hours would receive \$225. Participants will also receive up to \$300 in gender transition vouchers. Some intervention modules include homework: creating a budget, creating a resume, obtaining a professional-sounding email, creating a professional sounding voicemail. For each intervention group, participants who complete the homework for that session will have their name entered into a raffle for a \$20 gift card to a local vendor of the group's choosing.

We will also provide a meal at interventions sessions and may provide financial assistance for transportation costs.

For the employment assistance program, we will partially fund (offsetting \$3/hour for up to a 40 hours/week) an 8-week period during which participants would be hired on a temporary basis so employers have an opportunity to evaluate the participants' work. The goal with this approach is that some employers will hire participants after the end of the 2 months. So, employers would hire a participant at the normal starting wage and we would pay the employer \$3/hour for every hour the participant works up to 40 hours a week for up to 8 weeks. Note that this is directly paid to the employer rather than the participant.

In addition, during Aim 3, we will recruit a small number (N = 10 total, 5 in Richmond) of participants who report discrimination from religious communities to participate in a qualitative interview. This will last around 60-90 minutes and will ask about discrimination in religious settings. Individuals who participate will receive \$50.

2. If compensation will be pro-rated, explain the payment schedule.

For Aim 3, compensation for assessment completion will be prorated with 50% for completion of the subjective indicators, and 50% for completion of the objective indicators.

3. * Will Social Security Numbers be collected for compensation purposes only?

Yes
 No

ID: MS8_HM20011245

View: SF2 - Research Plan Complete

Research Complete

Protocol Progress:

? INITIAL SETUP
? BACKGROUND, RATIONALE & GOALS
? RESEARCH PLAN
? CONSENT PLAN
? RISKS, PRIVACY & CONFIDENTIALITY
? POPULATIONS WITH SPECIAL CONSIDERATIONS

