7. * Indicate if this study will have a Data Safety Monitoring Board (DSMB) or a Data Safety Monitoring Plan (DSMP): [Required for all greater than minimal risk studies]

DSMB

DSMP

No DSMB/DSMP [Note: This response is not applicable for greater than minimal risk studies]

8. * Describe your Data Safety Monitoring Plan for monitoring the study's data to ensure the safety of participants. This plan should include (but is not limited to) the following elements:

1. Who will monitor data
2. What data and/or processes will be reviewed
3. When and how frequently monitoring will occur
4. What report/documentation will be submitted to the IRB at the time of continuing reviews

See the help text for additional guidance.

A Serious Adverse Event (SAE) occurs when any one of the following events happens to a participant enrolled in our research protocol and is brought to the attention of anyone involved with the project: (1) death, (2) life-threatening injury or illness, (3) serious but not life-threatening injury or illness, or (4) participant becomes an immediate risk to the safety of self or others. If project staff become aware than any of these situations have occurred, we will report the

event as described below.

Within 48 hours of becoming aware of an SAE, we will report the event to the Virginia Commonwealth University and University of Missouri-St. Louis Institutional Review Boards as well as the NIH project officer for the study. The report will include a description of the SAE, including date, full chronology of the event based on information available to us, a determination of whether the SAE is related to the study procedures, the steps taken by our staff and/or others to address the SAE, an estimate of the likelihood of the recurrence of the SAE both for the participant and for other study participants, and a discussion of whether the event resulted in new information that indicate that the study procedures should be changed.

In addition to the immediate report of SAEs as described above, we will report any other (i.e., non-serious) adverse events on an annual basis to the Virginia Commonwealth University and University of Missouri-St. Louis Institutional Review Boards as well as the NIH project officer for the study. These steps for reporting SAEs and other adverse events are consistent with our IRB requirements for reporting adverse events.

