These data will be monitored by the PIs on an ongoing basis (at least monthly). We will monitor especially for adverse reactions to study materials or procedures and withdrawal from the study. We will report any adverse events and withdrawal from the study to the VCU IRB at continuing review.

ID: MS8_HM20011245

View: SF2 - Privacy

Privacy

Privacy refers to an individual's right to control how others view, record, or obtain information about them. When privacy is violated it can involve such things as

- Being asked personal questions in a public setting;
- Being publicly identified as having a particular characteristic or diagnosis;
- Being seen entering a place that might be stigmatizing;
- Being photographed, videotaped or observed without consent;
- Disclosure of personal information to unauthorized people

Privacy is not the same as confidentiality because privacy protections apply to people, and confidentiality protections apply to data. Confidentiality protections should be described on the Data Confidentiality page of this form, not here.

1. *** Describe how the research team will protect participants' privacy throughout the course of the study.**
Address privacy in the context of the following research activities as applicable:

- ***Identification of potential participants or secondary data/specimens of interest***
- ***Recruitment and screening activities***
- ***The informed consent process***
- ***Conduct of the study procedures***
- ***Data dissemination***

See the help text for additional guidance.

In-person recruitment will be conducted in environments where it will be likely to find TGW, including transgender health clinics, community events (e.g., ball celebrations), meetings at our partner NGOs, and commercial sex work areas. This is consistent with our prior work approved by this IRB. Individuals present in those environments will be eligible to complete the screening, including individuals who are not TGW (those individuals will be ineligible). Individuals who screen eligible will be asked if they are interested in participating in the larger study (Aims 1, 2, and 3) and, if so, will be asked to provide their first name and contact information (phone # and email address). In addition, individuals may contact us after learning of the study from the flyer, or Facebook page, or after receiving an email with the flyer from one of our community partners.

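### Adverse events are not actively solicited on the same schedule in both arms, and the monitoring plan does not name the systematic data already collected as an input

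*Combined protocol and SAP*

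**What the plan says.** **Monitoring plan** (Risks, Discomforts, Potential Harms and Monitoring, item 8). The serious-event definition lists four kinds of event and requires that the event "is brought to the attention of anyone involved with the project". The reporting clock also starts with staff knowledge: "Within 48 hours of becoming aware of an SAE, we will report the event". For everything else, "we will report any other (i.e., non-serious) adverse events on an annual basis". The principal investigators review at least monthly, and the stated focus is: "We will monitor especially for adverse reactions to study materials or procedures and withdrawal from the study".

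**Session contact.** In the Compensation section, the full intervention is "delivered over 6 days with 2 1/2 hour sessions per day, for a total of 15 hours". The Aim 3 e-mail script (Study Procedures, item 5) tells the other group: "If you are randomly assigned to receive the intervention in 6 months, you will come to three sessions on three different days". Item 7 calls this arm a wait-list minimal treatment control.

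**Contact common to both arms** (Study Procedures, item 7). Assessments take place at baseline, 3, 6 and 9 months and include the BSI-18, substance use, needle sharing and diagnosed sexually transmitted infection. For retention, "comprehensive tracking information will be collected and updated monthly". Home visits to verify housing are planned without restriction to one arm and without a stated number.

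**The concern.** The risks section names three kinds of harm: loss of confidentiality, distress or embarrassment from study topics, and raised anxiety about HIV. Behavioral Intervention Details adds that confidentiality cannot be guaranteed in a group. None of the measures described in Study Procedures asks whether any of these has happened because of the study. Knowledge of an event therefore depends on someone mentioning it or a staff member noticing it, and the sessions that give occasion for this fall at different times in the two arms.

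Two things are at stake. First, the monthly review may miss events that a direct question would bring out, in either arm. Second, if adverse events are later summarised by arm, the counts cannot be interpreted. The trial is meant to assess feasibility and supply parameters for later work, so a safety count that its successors cannot read is a real loss, though a modest one.

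**Working it through.** **1. Reproduce the plan's own figures.** Intervention sessions: 6 × 2.5 h = 15 h, as stated. Control workshop: 3 × 4 h = 12 h, as stated.

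**2. Trace how an event of each type would become known.**

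| Item | Method stated in the plan | Scheduled question? | Named as a monitoring input? |
|---|---|---|---|
| Serious adverse event | Comes to staff attention | None described | Yes, once known |
| Non-serious adverse event | None stated; annual report only | None described | Yes, once known |
| Withdrawal | Known from study conduct | Not needed | Yes |
| BSI-18 and risk-behaviour items | Computer measure, both arms, four assessments | Yes | No |

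Ascertainment is passive for serious events and unspecified for the rest. The systematic data exist but are not connected to the review.

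**3. Compare session contact before the control workshop.** Taking the workshop at six months, as the e-mail script does, the intervention arm has 6 sessions and the control arm 0. Assessments, home visits and tracking updates are planned for both arms.

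**4. Ask whether this yields a usable contact ratio.** It does not, because the result depends on what is counted:

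- Sessions plus baseline and month-3 assessments: (6 + 2) v 2, ratio 4.0.
- Sessions plus month 3 only: (6 + 1) v 1, ratio 7.0.
- Sessions, baseline and month 3, assuming one home visit per assessment: (6 + 4) v 4, ratio 2.5.
- After baseline and through the month-6 visit, with six monthly tracking updates: (6 + 2 + 6) v (2 + 6) = 14 v 8, ratio 1.75.
- Whole study, with sessions, workshop days and four assessments: (6 + 4) v (3 + 4) = 10 v 7, ratio 1.4.

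All variants exceed 1, but a contact ratio is not a detection ratio.

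**5. State what a passive count estimates.** Let r be an arm's true event rate over a window, d the probability that an event becomes known, and n the arm size (50 in each). The expected count is n × r × d, so the ratio of counts between arms is (r_I / r_C) × (d_I / d_C). Session attendance can raise both factors for the intervention arm. It can raise r because group disclosure and distress about session topics can arise in sessions, and d because staff are present. Only the product is observed. The documents give neither r nor d, so the two factors cannot be separated, and neither the size nor the direction of any bias in the comparison follows. Asking the same question at the same times in both arms brings the d terms closer together and lets the ratio speak more nearly to r.

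**The case against.** The case against is substantial, and much of it limits the point.

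- *Coming to attention is wider than being volunteered.* Staff are trained to respond to distress, facilitators complete a form after each session, recordings are sampled, and home visits and tracking contacts can reveal events. This stands: the serious-event sentence does not say that participants must speak up. But the forms and recordings arise from sessions, so they do not equalise the arms in the first six months.
- *The instruments are not reproduced.* The baseline and follow-up measure and the process measure for Aims 2 and 3 are listed as uploads only. This stands as a caveat. The process measure is described under Aim 2 as capturing reactions after each module; used that way in Aim 3, it would reach controls only at their workshop.
- *No comparison of adverse events by arm is planned.* True. The monitoring gap remains regardless, and the comparison matters only if counts are reported by arm.
- *Risk is low.* The study falls under expedited categories, and the plan cites more than 8,000 earlier participants with no adverse events reported. That bears on urgency, but the plan does not say how those events were sought.

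A reader might infer more than the documents support:

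- *That controls' harms are under-detected by some multiple, such as four.* That multiple is one count among several. Turning it into detection percentages needs an assumed probability per contact, and it would credit contacts with detecting events that had not yet occurred. Fewer reports from controls may also reflect less exposure.
- *That the monthly review has no systematic data.* Withdrawals are reviewed, and the BSI-18 is collected in both arms.
- *That a confidentiality breach would wait a year for action.* The annual interval is for reporting to the review boards and the NIH project officer. The principal investigators review at least monthly and may remove a participant who repeatedly violates confidentiality. The plan also states that its reporting steps meet the review boards' requirements.

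**Conclusion.** The point holds as a gap in ascertainment. The documents describe no active, common-schedule solicitation of adverse events. Serious events enter when staff learn of them, non-serious events have no stated collection method, and the monitoring plan does not name the BSI-18 or other systematic measures as inputs.

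With six sessions in one arm before the other arm's workshop, passive reports confound detection opportunity and exposure with true event rates. No numerical size can be attached to this, and the direction of bias in an arm comparison is not established.

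The conclusion rests on two assumptions. The control workshop must fall at about six months, a timing given only in the participant e-mail script; the Compensation section gives none, and item 7 times assessments as post-intervention. The uploaded instruments must contain no event items beyond what the protocol describes. If the first fails, the imbalance shrinks but the absence of solicitation remains. If the second fails, the main remaining task is to connect those items to the monitoring plan. The change is worth making, but it is not a flaw that prevents the trial from running.

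**What to change.** 1. Add the same short, fixed set of event items to the computer-administered measure at 3, 6 and 9 months in both arms: hospital care or serious injury; distress linked to the study; unwanted disclosure of participation or of information shared in a group; and violence, job loss or housing loss attributed to participation.
2. Add one open event question to the monthly tracking update already planned for participants.
3. In item 8 of the monitoring section, name these items and the BSI-18 as inputs to the monthly review, and state how non-serious events are collected.
4. Tabulate solicited events by arm over the same windows, separately from events volunteered or observed in sessions.

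A faster reporting route for confidentiality breaches is optional and is not needed to close this gap.

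The cost is a few survey items, one tracking question and revised monitoring text, with no added visits. The drawback is that more minor events will be recorded and reported.

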2. * To the best of your knowledge, do you (as PI) or any other engaged individual have a non-financial interest related to this study?

Non-financial interests could include such things as:

- utilizing your unlicensed intellectual property in the study,
- serving as an unpaid advisory board member or officer/director with a related entity, and
- equity or business ownership in a company that has yet to make a profit and is related to this project
- conflicts of time/effort,
- personal and professional relationships/affiliations,
- intellectual passions or personal beliefs
- other factors that could create bias in the study

Yes No**3. Describe any institutional conflict of interest that you or any member of the research team are aware of that pertains to this research:**

An institutional conflict of interest is a situation in which financial interests of the University or University leadership may affect research activities at VCU.

None

ID: MS8_HM20011245

View: SF2 - Other VCU Requirementsv2

Other VCU Requirements

This page asks questions on behalf of other ancillary offices, committees and departments at VCU regarding institutional requirements that could apply to this research. In some cases, these requirements could also impact the consent process or other aspects of the IRB's review.

Based upon answers provided earlier in this form, certain ancillary sections below may not have questions displayed if those requirements are not applicable to this study.

1. Cost Coverage Analysis

Information on coverage analysis requirements and processes can be found through VCU's Clinical Research Compliance Program at https://research.vcu.edu/compliance_program/research_coverage.htm

1. * VCU requires that all clinical research studies be evaluated to determine if a Coverage Analysis is required. Has your study been evaluated by an institutionally designated Coverage Analysis Specialist? Yes No Not Applicable**2. ClinicalTrials.gov Program & OnCore**

For guidance, see <https://ccctr.vcu.edu/support/clinical-trials/clinicaltrialsgov.html> or email [contact]

1. * Is this a Clinical Trial? Yes No**2. * The PI acknowledges awareness of the following requirements for posting clinical trial consent forms:**

- Each clinical trial under the 2018 Common Rule that is conducted or supported by a Federal department or agency must post one IRB-approved consent form that was used to enroll subjects on a publicly available Federal website [45 CFR 46.116(h)].
- When engaged in multi-site research, the VCU PI is responsible for confirming with the lead site who is responsible for posting the informed consent form.
- When VCU is the lead site, the VCU PI is responsible for posting the informed consent form (unless the federal department or agency will post it).

 Yes No**3. Community Engagement**

For more information, see <https://community.vcu.edu/>

1. * Is there a community partner in this research study?

Yes No

2. * Provide details about each community partner. If there are more than 5 community partners, add the 5 most significant partners.

Organization	Code / Country	Zip	Role
Nationz Foundation	23227		Provides guidance to the researcher about the study design, subject recruitment, data collection, or data analysis. Partner does NOT make decisions about study design.
Health Brigade	23230		Provides access to study subjects or project sites only. Partner is not involved with study design, subject recruitment, data collection, or data analysis
Minority Health Consortium	23219		Provides guidance to the researcher about the study design, subject recruitment, data collection, or data analysis. Partner does NOT make decisions about study design.

4. Family Educational Rights and Privacy Act (FERPA) Requirements

For guidance, see <https://rar.vcu.edu/records/family-educational-rights-and-privacy-act/>

1. * Does this study involve obtaining information from VCU students' educational records (see help text)?

 Yes No

5. General Data Protection Regulation (GDPR) Requirements

Contact the VCU Research Data Privacy Office with questions about GDPR requirements:

https://research.vcu.edu/data_privacy

1. * Does this study involve the VCU site, or any sites under the VCU IRB's oversight, obtaining data in, or from, the European Economic Area? (see Help Text for list of countries included in the EEA)

 Yes No

6. Information Security

For guidance, see <https://ts.vcu.edu/askit/essential-computing/information-security/>

1. * Using the VCU Data Classification Tool, please determine the appropriate data classification category for the data that will be collected or used in this research.

Note: if the data falls into Category 1, a data security management plan is required by University Information Security Office.

See help text for information on accessing the VCU Data Classification Tool, and for information on creating a data security management plan.

- Category 1: all data that require breach notifications in the event of improper release, including all non-publicly available personally identifiable information covered by HIPAA and Commonwealth of Virginia regulations.
- Category 2: all proprietary data that if improperly released has the potential to cause harm to the institution, its mission or its reputation that do not require breach notifications.
- Category 3: all non-proprietary data that is considered publicly available for unrestricted use and disclosure. Such information is available to all members of the University community and to all individuals and entities external to the University.

2. * I confirm use of the VCU Data Classification Tool in determining the data classification category selected in Question 1:

Yes
 No

7. Massey Cancer Center Protocol Review and Monitoring Committee (PRMC)

For guidance, see <https://www.massey.vcu.edu/research/protocol-review/>

1. * Does this study target any of the following populations?

- cancer patients,
- family members of cancer patients,
- cancer healthcare providers, or
- cancer prevention where cancer is integral to the research question

Yes
 No

8. VCU Health Department of Patient Centered Services

1. * Does your study involve a satisfaction survey administered to VCUHS patients (*See Help Text):

Yes
 No
 Not Applicable

9. VCU Faculty-Held IND or IDE

For guidance, see <http://go.vcu.edu/indide>

10. VCU Health System locations

1. * Will research activities occur in patient care areas of the VCU Health System (including at CHoR, Community Memorial Hospital, VCU Medical Center and Massey Cancer Center)?

Yes
 No

11. VCUHS Department of Pathology

Learn more about requesting and establishing an account with Pathology here: See <https://pathology.vcu.edu/research-services/>

12. VCU Institutional Biosafety Committee (IBC)

To contact the Biosafety Office, call [contact] or extension [name], or view their website at: <https://research.vcu.edu/ibc>

1. * Does this project involve the use of Bio-Hazardous Substances such as gene transfer, use of organisms or their products, biological toxins, and/or viruses?

Yes
 No

2. * Does this project involve recombinant DNA (rDNA) and/or synthetic nucleic acids?

Yes
 No

13. VCU Radiation Safety Committee (RSC)

For contact the Radiation Safety Section, call [contact], or view their website at: <https://research.vcu.edu/rsc>

1. * Does this study involve radiation exposure and/or scans involving radiation (e.g.: PET, MRA, CT, DXA, nuclear medicine, etc.)?

Yes

No

14. Virginia-Stem Cell Research Oversight (SCRO)

For guidance, contact the Office of Research Integrity and Ethics (ORIE) at: [contact]

1. * Does this study involve stem cells?

Yes

No

15. VCU Scientific Review Committee (SRC)

For guidance, see <https://cctr.vcu.edu/support/study-participation-recruitment/scientific-review>

1. * Has this human subjects protocol (not the grant application) already been reviewed by the funder of a sponsored project (e.g. a federal, state or non-profit funding sponsor)?

Yes

No

16. Upload any documents requested in the questions above:

ID: MS8_HM20011245

View: SF2 - Institutional Requirements Complete

Institutional Requirements Complete

Protocol Progress:

? INITIAL SETUP
 ? BACKGROUND, RATIONALE & GOALS
 ? RESEARCH PLAN
 ? CONSENT PLAN
 ? RISKS, PRIVACY & CONFIDENTIALITY
 ? POPULATIONS WITH SPECIAL CONSIDERATIONS
 ? INSTITUTIONAL REQUIREMENTS
 ? DOCUMENTS

Click Continue below to go to the next section

ID: MS8_HM20011245

View: SF2 - Documents

Documents

1. Upload any documents that the VCU IRB will need to conduct a review of this submission:
 A list of potential documents is given in the help text.

NOTE: The delete function should only be used if an incorrect document is uploaded or added to the system AND that document has not been reviewed and approved by the IRB. Do NOT delete documents that the IRB previously reviewed and approved.

Once you have uploaded a document to RAMS-IRB, any changes to that document (i.e. different versions of

the same document) should be added to the IRB submission by using the Update button. To provide updated documents, follow these steps:

- Click the **Update** button located to the left of the document to be updated.
- In the Add Document window, click the **Choose File or Browse** button, select the file you are adding, and click on the **Open** button.
- Click **OK** to close the Add Document window, and the system will upload the revised document. RAMS-IRB will automatically provide a version number for the document.

To access previous versions of a document in RAMS-IRB you must use the History link associated with the document.

- Click the **View or Update** button located to the left of the document you wish to access.
- In the Add/View Document window, click the "History" hyperlink located to the right of the file name.
- A separate window will open that shows all versions of the document that have been added to RAMS-IRB. Click on any file name to download and view the document.

Document Name	Document	Version	Date Modified	Uploaded By	Type	Approved
View Consent - Aim 3 RCT	HM20011245 Aim 3 consent form final.03.17.2020.pdf	0.07	3/23/2020 10:07 AM	[name]	Consent/Assent/Information Sheet	Yes
View Consent - Qualitative interview assessing religious discrimination	HM20011245 Consent form for qualitative interview regarding religious discrimination.pdf	0.02	3/23/2020 10:07 AM	[name]	Consent/Assent/Information Sheet	Yes
View E-mail recruitment script - Aim 3	Aim 3 email script.03.17.2020.docx	0.02	3/17/2020 3:39 PM	[name]	Recruitment/Advertising	Yes
View Phone recruitment script - Aim 3	Aim 3 Telephone script.03.17.2020.docx	0.02	3/17/2020 3:39 PM	[name]	Recruitment/Advertising	Yes
View Qualitative interview guide (Aim 3)	Interview Guide for Measuring Participants Experiences of Religious Discrimination - Aim guide (Aim 3) 3.docx	0.01	3/17/2020 3:13 PM	[name]	Research Measure	Yes
View Screening Survey - Aim 3	Screening Survey - HM20011245.Aim 3 final.docx	0.02	3/4/2020 3:13 PM	[name]	Research Measure	Yes
View Intervention Manual (Intro, Modules 1, 2,3, 5)	Integrated Intro.Modules.1.2.3.5.Aim3 March 2020.docx	0.03	3/4/2020 1:34 PM	[name]	Research Protocol	Yes
View Quantitative Measure for Baseline and follow-up	Baseline Measure.final.docx	0.02	3/2/2020 3:42 PM	[name]	Research Measure	Yes
View Budget Worksheet for use with module 3	pdf-1020-make-budget-worksheet(1).pdf	0.01	12/20/2019 12:11 PM	[name]	Research Protocol	Yes
View Intervention Manual - Module 4	FINAL_Module 4_Aim 3.docx	0.02	12/20/2019 12:06 PM	[name]	Research Protocol	Yes
View Aim 2 and 3 process measure	Process Measure.docx	0.03	12/19/2019 3:04 PM	[name]	Research Measure	Yes
View Consent -	HM20011245 Aim 2 consent form version 2	0.06	8/8/2019	[name]	Consent/Assent/Information	Yes

Aim 2 pilot test	clean copy 8.7.2019.pdf		11:32 AM	[name]	Sheet	
View	Session reminder scripts	Session Reminder Scripts.docx	0.01	8/1/2019 3:31 PM	[name]	Recruitment/Advertising Yes
View	Sample Cover Letter	Sample Cover Letter.docx	0.01	8/1/2019 3:13 PM	[name]	Other Yes
View	Sample Resume #3	Functional Resume Example.docx	0.01	8/1/2019 3:13 PM	[name]	Other Yes
View	Sample Resume #2	Combination Resume Example.docx	0.01	8/1/2019 3:13 PM	[name]	Other Yes
View	Sample Resume #1	Chronological Resume Example .docx	0.01	8/1/2019 3:12 PM	[name]	Other Yes
View	CDC Needle Cleaning Procedures	cdc-hiv-clean-your-syringes.pdf	0.01	8/1/2019 3:10 PM	[name]	Other Yes
View	E-mail recruitment script - Aim 2	E-mail script Aim 2.docx	0.01	6/26/2019 2:15 PM	[name]	Recruitment/Advertising Yes
View	Phone Recruitment Script - Aim 2	Telephone script Aim 2.docx	0.01	6/26/2019 2:15 PM	[name]	Recruitment/Advertising Yes
View	Screening Survey for Aim 2	Screening Survey - HM20011245.v4.docx	0.01	6/26/2019 2:13 PM	[name]	Research Measure Yes
View	Consent - Aim 2 Screening Survey	HM20011245 ConsentForm_Screening Survey_Aim 2.docx	0.01	6/26/2019 1:34 PM	[name]	Consent/Assent/Information No Sheet
View	Consent - Aim 1 Screening Survey	HM20011245 ConsentForm_Screening clean copy.pdf	0.11	8/14/2018 9:44 AM	[name]	Consent/Assent/Information No Sheet
View	Consent - Aim 1 Qualitative Interview-TGW	Consent - Qualitative Interview for transgender women - HM20011245.v6.pdf	0.09	8/14/2018 9:44 AM	[name]	Consent/Assent/Information No Sheet
View	E-mail Script Screening Assessment	E-mail script screening assessment.docx	0.01	8/13/2018 1:42 PM	[name]	Recruitment/Advertising Yes
View	Facebook Page appearance	TWHealth Facebook page appearance.docx	0.01	8/13/2018 1:04 PM	[name]	Recruitment/Advertising Yes
View	Phone recruitment script	Telephone script.v2.docx	0.02	8/13/2018 1:04 PM	[name]	Recruitment/Advertising Yes
View	E-mail recruitment script	E-mail script.v3.docx	0.03	8/13/2018 1:03 PM	[name]	Recruitment/Advertising Yes
View	Aim 1 Screening	Screening Survey - HM20011245.v3.docx	0.03	7/24/2018 1:51 PM	[name]	Research Measure Yes

Survey

View	Flyer	TWHealth Flyer_07192018.docx	0.01	7/24/2018 1:51 PM	[name]	Recruitment/Advertising	Yes
View	Consent - Aim 1 Qualitative Interview - Key Informants	Consent - Qualitative Interview for key informants - HM20011245.v3 clean version.pdf	0.06	5/7/2018 2:24 PM	[name]	Consent/Assent/Information No Sheet	
View	Aim 1 Interview Guide - Community Financial Partners	Interview Guide for Community Financial Partners Staff - HM20011245.docx	0.01	4/2/2018 2:02 PM	[name]	Research Measure	Yes
